## **5 STUDY INTERVENTION**

### **5.1 Concomitant Medications/Treatments**

All concomitant medications will be recorded on a study CRF for each subject. The information about these medications will be collected and recorded prior to enrollment. If subjects are enrolled on a date prior to the ablation procedure, the concomitant medications will be reviewed and updated with the subject for accuracy during the first study visit and prior to the surgical intervention utilizing the Vestico Device.

### **5.2 Administration of Intervention**

The Vestico device will be utilized during the RFA at the one clinic in the United States and the intervention will be performed by the qualified study investigators trained in the use of the Vestico device. This intervention will occur at one visit only and should take approximately two hours.

### **5.3 Accountability Procedures for the Study Product**

The sponsor, Venclose, Inc., will supply the Vestico Devices to the clinical site at no charge. Supply of the consumable (Vestico Catheter) and reusable (Vestico Generator) components will also be provided at no charge in sufficient quantity to meet the requirements of the study.

The study CRFs include capture of serial, batch/lot numbers of components used for each study subject. These will be compared to unused and returned supply at study close to ensure that each consumable and reusable component is accounted for.

#### **5.3.1 Deficient Product**

If a device deficiency is detected, the investigator will discontinue use of the affected component and report this deficiency immediately to the study sponsor.

The study sponsor will investigate and determine corrective or preventive actions if required.

Additional supplies may be requested in writing to the study sponsor if deficiencies require replacement of the device or its consumable or reusable components.

### **5.4 Procedures for Training Investigators and Study Monitoring**

Investigators will have documented certification of GCP training.

Investigators will receive practical training for the Vestico Device that will be conducted by qualified Venclose training personnel according to Venclose's approved customer training procedure. Prior to site initiation, training of the investigators and assistants will be provided by the sponsor and Principal Investigator and will cover the following: study protocol, Investigator

and Sponsor responsibilities, and site procedures. A follow up training session to review these materials will be conducted at site initiation by the clinical study monitor and Venclose Training personnel. Training records will be created for each trainee.

Only registered investigators and assistants who have documented training in GCP, have received the required study related training, and are determined to be proficient in the use of the Vestico device will participate in the conduct of the study.

A qualified clinical study monitor will verify collection of data, and monitor compliance to the protocol and study procedures. The monitor is required to report any deviations from the site procedures or study protocol to the sponsor and Principal Investigator.

Venclose Service and Support technicians may be on-site to provide technical support to the clinician, should they request it. The Service and Support personnel will not be involved in the planning or be present in the operatory during the procedure to ensure that data recorded is not compromised.

## 6 STUDY PROCEDURES

### 6.1 Subject Recruitment

Potential study subjects may be identified through in-clinic advertising in the form of a flyer posted in high visibility areas. Interested potential participants may approach clinic staff to express their interest and receive Informed Consent information. Patients who are being consulted for treatment of their varicose veins may also be informed by their attending physician that the study is taking place and if interested, an Informed Consent appointment can be booked with the Investigator or his/her designate.

### 6.2 Informed Consent

The informed consent visit will be conducted by the Investigator or their designated study staff at the time of the consultation for intervention visit and may occur up to one month before the scheduled intervention.

- Review all aspects of the clinical investigation that are relevant to the possible subject's decision to participate
- Care is to be taken not to coerce or unduly influence possible subject participation
- Provide ample time for the possible subject to read and understand the informed consent form and to consider participation
- Answer all questions asked to the satisfaction of the possible subject
- Provide a copy of the signed informed consent to the possible subject, if signed
- Arrange for Screening / Enrollment Visit

A copy of the IRB approved Informed Consent Form is located in Appendix B of this document.

### 6.3 Costs to Subjects and Payment for Participation

There will be no cost to subjects as a result of participating in this study. Participants will receive a \$75-\$150 pre-loaded gift card for each completed study visit to cover travel and out-of-pocket expenses related to the study.

### 6.4 Consultation / Enrollment

Consultation Visit (up to two months before the scheduled intervention)

- Confirm documented informed consent from potential subject
- Obtain/review medical/clinical history (standard of care)
- Assess/review eligibility based on inclusion/exclusion criteria
- Review concomitant medications history to determine eligibility based on inclusion/exclusion criteria (standard of care)

- Perform medical/clinical examinations needed to determine eligibility (standard of care)
- Obtain demographic information (standard of care)
- Determine surgical site(s)
- Pre-operative Duplex Ultrasound Scan
- Schedule study intervention visit for individuals who are eligible and available for the study (standard of care)
- Complete Screening CRF
- Provide potential subjects with instructions and possible prescriptions needed to prepare for the intervention visit (standard of care)

## **6.5 Baseline / Intervention**

Baseline Visit (Day of intervention)

- Verify inclusion/exclusion criteria
- Review concomitant medications (standard of care)
- Record results of physical and clinical examinations (standard of care)
- Complete Baseline CRFs
- Perform ablation procedure (standard of care) using the Vestico Device
- Post-operative Duplex Ultrasound Scan (same day and within 3 days of Intervention)
- Record AEs and SAEs and report to sponsor immediately (if applicable)

## **6.6 3-day Post-Intervention Safety Assessment**

Follow-up Visit (3-days post-intervention)

- Document all adverse events, if any
- Post-operative Duplex Ultrasound Scan (same day or within 3 days of 3-day Follow-up)

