**Primary Endpoints:**

- 1) Safety - Procedure related adverse events (AE), serious adverse events (SAE), adverse device effects (ADE), serious adverse device effects (SADE) and unanticipated adverse device effects (UADE) will be monitored 3 days, 15 days (+/- 3 days), and 30 days (+/- 3 days) post-procedure and analyzed for acceptability post study .

Monitored events include:

- Edema
- Skin changes
- Venous ulcers
- Deep vein thrombosis
- Superficial vein thrombosis
- Pulmonary embolism
- Venous thromboembolism
- Skin burn
- Thermal injury of adjacent tissues
- Paresthesia
- Infection/cellulitis
- AV Fistula
- Need for re-operation
- Death

- 2) Effectiveness - Technical success, defined as successful access and entry into the IPV to be ablated and the ability to deliver the intended energy to the target vein segment, will be evaluated.

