**Secondary Endpoints:**

- 1) The acute ablation success endpoint is defined as complete lack of flow or IPV disappearance in the treated segment (vessel occlusion). Success will be measured by Duplex Ultrasound imaging performed 3 days, 15 days (+/- 3 days), and 30 days (+/- 3 days) post-procedure.
- 2) Presence of reflux in the treated IPV will be recorded at each time point (3, 15, and 30 days post intervention) and an overall

absence of reflux rate (i.e. reflux free rate) will be documented at each follow-up time point

[figure not shown]

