###### Secondary Endpoints:

- 1) The acute ablation success endpoint is defined as complete lack of flow or IPV disappearance in the treated segment (vessel occlusion). Success will be measured by Duplex Ultrasound imaging performed 3 days, 15 days (+/- 3 days), and , and 30 days (+/- 3 days) post-procedure.

- 2) Presence of reflux in the treated IPV will be recorded at each time point (3, 15, and 30 days post intervention) and an overall absence of reflux rate (i.e. reflux free rate) will be documented at each follow-up time point

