## **8.2 Time Period and Frequency for Event Assessment and Follow-Up**

Any unanticipated problems, adverse events and/or serious adverse events will be recorded in the subject CRF during the study. The PI will record all reportable events with start dates occurring any time after informed consent is obtained until 30 days after the last day of the study participation. The investigator will inquire about the occurrence of AE/SAEs since the last visit. Events will be followed for outcome information until resolution or stabilization.

CONFIDENTIAL

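### The protocol specifies no prompted present/absent check of the 14 monitored safety events at days 3, 15 and 30, so mild events may be under-recorded

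*Combined protocol and SAP*

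**What the plan says.** Safety is the first primary endpoint. In the Clinical Protocol Summary, procedure-related adverse events and device effects "will be monitored 3 days, 15 days (+/- 3 days), and 30 days (+/- 3 days) post-procedure and analyzed for acceptability post study". A list of 14 items follows, introduced by "Monitored events include"; section 3.1 repeats it. No item is given a definition, a grade or a method of detection.

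Sections 6.6, 6.7 and 6.8 are headed as safety assessments. Each contains two tasks: "Document all adverse events, if any", and a duplex scan. Sections 2.2 and 3.2 B also call for a safety assessment without saying what it consists of. The stated method is in section 8.2: "The investigator will inquire about the occurrence of AE/SAEs since the last visit".

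Examinations appear at the consultation visit (section 6.4, for eligibility) and on the intervention day (section 6.5: "Record results of physical and clinical examinations (standard of care"). None is listed at follow-up.

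The follow-up duplex serves the secondary endpoints. For occlusion, "Success will be measured by Duplex Ultrasound imaging performed 3 days, 15 days (+/- 3 days), and 30 days (+/- 3 days) post-procedure"; reflux in the treated vein is recorded at the same visits. Section 3.2 B(v) likewise speaks of flow and reflux ceasing.

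Section 3.2 D gives adverse events one open entry in the list of data collected. Section 11.1 has a general missing-at-random assumption and no rule for an empty adverse event field.

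**The concern.** The plan names specific events as its primary safety measure but does not carry that list into the visits where the events would be found. Several items, such as edema, skin change, a small burn and paresthesia, tend to surface only if someone looks at the limb or asks about them by name. A general question may not bring them out.

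The direction of the error matters. The working hypothesis is that the device causes no adverse outcomes (Clinical Protocol section) or no significant ones (sections 2.2 and 3.1), so a low count is the favourable result. The study has one site and one planned investigator (section 3.2 E), with no control arm described. The investigator role that treats also asks about events, and no independent event assessment is specified. Section 11.3 leaves the judgement of adverse events to a post-hoc review with no threshold, and the data go into a premarket notification. With no comparator that would share the same under-recording, the conclusion depends on how completely events are captured.

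There is also an attribution problem. Section 2.1 describes edema, skin changes and ulceration as manifestations of advanced venous disease. Without a status at baseline and at each visit, a new or worse finding cannot be told from an old one.

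**Working it through.** There is no figure in the plan to reproduce: section 11.3 states that no formal sample size calculation was made, and no expected event rate or margin is given. The check has two parts.

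**1. The 14 events against the follow-up procedures.**

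| Events | How they would be found | What 6.6 to 6.8 and 8.2 direct |
|---|---|---|
| Edema, skin change, ulcer, skin burn, thermal injury, paresthesia, infection (7) | Looking at the limb or asking by name | General inquiry; no examination listed |
| DVT, superficial thrombosis, AV fistula (3) | Can be read from duplex | Scan done, but stated outcomes are occlusion and reflux |
| Pulmonary embolism, venous thromboembolism, re-operation, death (4) | History or records | General inquiry; death and re-operation unlikely to be missed |

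The gap is clearest for the seven events in the first row. For the three in the second row the measurement is already made, but no one is directed to record the finding.

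**2. Scale, for illustration.**

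Inputs: n = 20 or 30 subjects (section 11.3). The true per-subject rate p of one event type and the share s of affected subjects whose event is recorded over all three visits are assumptions, not document figures.

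Formula: P(none recorded) = (1 − p × s)^n.

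| p | s | n = 20 | n = 30 |
|---|---|---|---|
| 10% | 100% | 0.90^20 = 0.122 | 0.90^30 = 0.042 |
| 10% | 80% | 0.92^20 = 0.189 | 0.92^30 = 0.082 |
| 10% | 50% | 0.95^20 = 0.358 | 0.95^30 = 0.215 |
| 5% | 100% | 0.95^20 = 0.358 | 0.95^30 = 0.215 |
| 5% | 50% | 0.975^20 = 0.603 | 0.975^30 = 0.468 |

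At p = 10%, halving capture multiplies the chance of a clean record by 0.358 / 0.122 = 2.9 (n = 20) or 0.215 / 0.042 = 5.1 (n = 30). At 80% capture the effect is much smaller.

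The same point can be put as a bound. With none recorded, the exact one-sided 95% upper limit on the rate of recorded events is 1 − 0.05^(1/n): 13.9% for n = 20 and 9.5% for n = 30. If only half of events are recorded, the limit on the true rate is that figure divided by 0.5: 27.8% and 19.0%.

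**The case against.** The strongest reply is that the duty to look is already there. The endpoint says the events are monitored at these visits, the visits are headed as safety assessments, and an instruction to document all adverse events covers the 14. This stands in part: the obligation exists. What is missing is a stated method for meeting it.

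Second, the case report forms are not reproduced and may already hold a checklist. Sections 9, 10 and 12.6 provide for monitoring against missing data, verification of required data elements and query resolution. This also stands, and it limits the conclusion to what the protocol specifies. Those controls can enforce a per-event record only if one is required somewhere.

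Third, the illustration rests on assumed values. It treats one event type rather than the whole list, and the plan sets no zero-event success rule. Three visits also give three chances: an event persisting through all of them, with an independent 50% chance of being picked up each time, would be found with probability 1 − 0.5^3 = 87.5%. This is fair. Half capture suits transient or consistently unasked events better than lasting ones.

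A reader might also infer stronger statements that the documents do not support:

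- That events are sought by open inquiry alone. A duplex scan is done at every follow-up visit and may reveal thrombosis or AV fistula.
- That mild events will be missed. The documents give nothing on how sensitive the inquiry is; this is a risk, not a finding.
- That an empty form counts as event-free. No rule says so; the status of a blank is simply undefined.
- That the only examination is on the intervention day. Section 6.4 lists one at consultation; the gap is at follow-up.

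**Conclusion.** The concern holds as a gap in how the primary safety endpoint is measured. For days 3, 15 and 30 the protocol specifies no prompted record of the 14 events, no limb examination, no reading of the scan for thrombosis or AV fistula, and no way to tell an absent event from an unassessed one. Mild events found by looking or asking may be under-recorded, in the direction that favours the device.

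The size cannot be known from the documents. Over the assumed range (true rate 5% or 10%, capture 50% to 100%), the chance of recording none of a given event runs from 12% to 60% with 20 subjects and from 4% to 47% with 30. These figures show only that a zero count is hard to interpret when capture is unknown. They do not show that capture will be poor.

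If the case report forms already contain a per-event checklist, what remains is to require it in the protocol and to settle baseline status and the handling of unassessed items.

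**What to change.** In sections 6.6 to 6.8, replace the open instruction with a prompted Yes / No / Not assessed record of each monitored event at each visit, followed by an open question for anything else.

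- Record per treated limb: edema, skin change, ulcer, burn, thermal injury, paresthesia, infection, DVT, superficial thrombosis and AV fistula.
- Record per subject: pulmonary embolism, venous thromboembolism, re-operation and death.
- At the section 6.5 visit, record baseline status of edema, skin change, ulcer and paresthesia. Count only new or worsened findings at follow-up, and record relatedness, since the endpoint is procedure-related events. Without this, prompting would count existing disease as safety events.
- Score DVT, superficial thrombosis and AV fistula from the duplex already scheduled, with a field for each on the scan form.
- In section 11.1, state that Not assessed is analysed as missing, not as event-free.

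The cost is one extra form page and a few minutes at visits already planned, with no added visits, scans or subjects. The downside for the sponsor is that more mild events will probably be reported, so the safety result may look less favourable. If the existing forms already do this, a reference to them in sections 6.6 to 6.8 is enough for the recording part.

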## **6.7 15-day Post-Intervention Safety Assessment**

Follow-up Visit (15-days post-intervention)

- Document all adverse events, if any
- Post-operative Duplex Ultrasound Scan (same day or within 3 days of 15-day Follow-up)

## **6.8 30-day Post-Intervention Safety Assessment**

Follow-up Visit (30-days post-intervention)

- Document all adverse events, if any

- Post-operative Duplex Ultrasound Scan (same day or within 3 days of 30-day Follow-up)

## **6.9 Withdrawal Visit**

Any subjects wishing to withdraw or be withdrawn by the clinician will be scheduled for a withdrawal visit. Reasonable efforts will be made to ascertain the reason for withdrawal which will be documented in the subject's CRF. However, the study subject is not obligated to provide a reason for their withdrawal. Withdrawals will be reported to an accredited IRB per their guidelines.

## **6.10 Unscheduled Visit**

Subjects in need of a visit between the screening and baseline visits will be scheduled and any treatment or evaluation will be documented in a study CRF if they have not completed the baseline visit.

## 7 STUDY SITE SELECTION

### 7.1 Site Selection

Site will be selected based on the following criteria:

- i. Geographic location;
- ii. Expertise in therapeutic area;
- iii. Level of experience and training (clinic, research, etc.);
- iv. Availability of appropriate type and number of subjects;
- v. Adequate facilities, staff, resources; including an on-site Duplex Ultrasound Scanner;
- vi. No undisclosed financial or professional conflict of interest with the proposed study; and
- vii. The investigator is not the subject of current investigation or review by their licensing organization or other regulatory body.

## 8 ASSESSMENT OF SAFETY

### 8.1 Reporting Procedures

#### 8.1.1 Reportable Events and Unanticipated Problems, Reporting to FDA and IRB

A reportable event is defined as anything that could significantly impact the conduct of the research or alter the Institutional Review Board's (IRB) approval or favorable opinion to continue the research.

An unanticipated problem is defined as any incident, experience, or outcome (including an adverse event) that meets all of the following criteria:

- **Event is unexpected** (in terms of nature, severity, or frequency) given (a) the research procedures that are described in the protocol-related documents, such as this IRB approved research protocol and informed consent document, or the Device Instructions for Use; (b) the event is not associated with the expected natural progression of any underlying disease, disorder, predisposing risk factor, or condition of the participant(s) experiencing the adverse event; and
- **Related or possibly related** to participation in the research (possibly related means there is a reasonable possibility that the incident, experience, or outcome may have been caused by the investigational product(s) or procedure involved in the research); and
- Suggests that the research places subjects or others at a greater risk of harm (including physical, psychological, economic, or social harm) than was previously known or recognized.

Should an unanticipated problem, or reportable event occur due to participation in this study, the information will be recorded in the subject CRFs and reviewed by the sponsor.

#### **Adverse Events or Serious Adverse Events that are Unanticipated Problems**

NOTE: Report to the IRB only adverse events that in the opinion of the investigator may represent unanticipated problems involving risks to the other subjects in the research.

The investigator must immediately inform the sponsor of any unanticipated problems, adverse events and/or serious adverse events. The investigator is responsible for reporting adverse events without delay to the IRB that fit the above criteria.

## **8.2 Time Period and Frequency for Event Assessment and Follow-Up**

Any unanticipated problems, adverse events and/or serious adverse events will be recorded in the subject CRF during the study. The PI will record all reportable events with start dates occurring any time after informed consent is obtained until 30 days after the last day of the study participation. The investigator will inquire about the occurrence of AE/SAEs since the last visit. Events will be followed for outcome information until resolution or stabilization.

CONFIDENTIAL

## **9 STUDY OVERSIGHT**

In addition to the responsibility of the principal investigator to oversee study conduct, an independent clinical study monitor will conduct routine monitoring visits to minimize the instances of errors or missing data, to provide assurance that the study documentation is completed according to procedures and to assess compliance with the protocol, GCPs and intended use of the device. (See section 11.)

CONFIDENTIAL

## **10 CLINICAL SITE MONITORING**

Clinical site monitoring is conducted to ensure that the rights of human subjects are protected, that the study is implemented in accordance with the protocol and/or other operating procedures, and that the quality and integrity of study data and data collection methods are maintained. Monitoring for this study will be performed by a qualified individual independent of the study. The monitor will evaluate study processes and documentation based on International Conference on Harmonization (ICH), E6: Good Clinical Practice guidelines (GCP).

Some monitoring activities may be performed remotely, while others will take place at the study site(s). The independent monitor will conduct monitoring activities and provide reports of the findings and associated action items to the site study team, the study PI and the sponsor. The clinical study monitor will conduct routine monitoring visits and will verify the collection of required data elements. Additional monitoring will be done at the discretion of the Sponsor and clinical study monitor.

